6.3 Analysis of Safety Data

The Safety Evaluation Set will be used for all safety analyses. All safety parameters will be presented descriptively and as data listings. Continuous variables will be summarized using descriptive summary statistics such as mean, median, standard deviation, minimum and maximum. Categorical variables will be summarized as counts and percentages. Unless otherwise specified, at each level of subject summarization, a subject will be counted only once. If there is more than one occurrence of an event, the event of the worse severity or the worst-case relationship category will be summarized.

6.3.1 Adverse Events

Adverse events will be coded using MedDRA dictionary (Version 20.0) and will be classified by system organ class (SOC) and preferred term (PT). Adverse events meeting certain criteria as defined in Section 9.7 of the protocol and Section 7 below will be adjudicated by the Clinical Events Committee and be designated a Major Complication, Minor Complication, or VARC-2 Major Vascular Complication for the primary and secondary safety endpoints as applicable.

6.3.2 Primary Safety Endpoint:

The Major Complication rate is defined to be the proportion of subjects in the safety evaluation set with one or more Major Complications. The Major Complication rate will be presented along with the one-sided upper 97.5% confidence bound. If this confidence bound is less than 19.9%, the study will have met its primary safety objective.

If a significant number of subjects (>5%) are lost to follow-up or die due to a reason other than a major complication, the Major Complication rate will also be estimated as a Kaplan-Meier rate. Subjects lost to follow-up will be censored at the date of their last contact. Subjects who die due to a reason other than a Major Complication will be censored at their date of death. An exact one-sided upper 97.5% confidence bound will be placed on the estimated major complication rate at 30 days using the formula given by Peto, Peto, and Armitage⁴. If this upper confidence bound is less than 19.9%, the study will have met its primary safety objective.

Additionally, the proportion of subjects with each individual Major Complication will be presented along with their two-sided exact 95% confidence intervals.

6.3.3 Secondary Safety Endpoint:

The proportion of subjects with Minor and Major VARC-2 complications will be presented. Minor complications will be qualitatively evaluated against the CAC of 20%. Summary statistics will be reported, but no formal statistical test will be performed.

Additional Safety analyses will report the incidence of adverse events:

- Overall (i.e., regardless of severity or relationship to procedure or device)
- By severity grade as determined by the Investigator (mild, moderate, or severe):
 - **Mild:** awareness of a sign or symptom that does not interfere with the subject's usual activity or is transient, resolved without treatment and with no sequelae.
 - **Moderate:** interferes with the subject's usual activity and/or requires symptomatic treatment.
 - **Severe:** symptom(s) causing severe discomfort and significant impact on the subject's usual activity and requires treatment.
- By relationship to the device and by relationship to the procedure as determined by the Investigator:
 - **Not Related:** An AE which cannot be attributed to the study device or initial study procedure.

⁴ Peto R, Pike MC, Armitage P, et al. *op cit.*

- **Unknown Relationship:** The relationship of the AE to the device or procedure cannot be determined.
- **Possible:** The clinical event occurs within a reasonable time sequence to study procedure/study device and there is some evidence to “possibly” suggest a causal relationship. However, the influence of other factors such as underlying disease, concomitant medications, or concurrent treatment may have contributed to the event.
- **Probable:** The temporal sequence between the device use or procedures and the event is such that the relationship is likely or subject’s condition or concomitant therapy could have caused the AE.
- **Definite:** The clinical event occurs in a plausible time relationship to study procedure/study device and cannot be explained by any concurrent disease or other devices, drugs or chemicals.

Adverse events with relatedness categorized as possible, probable, or definite will be considered “device-related” or “procedure-related” as appropriate.

Overall frequency and the frequency of Major Complications, Minor Complications, and VARC-2 Major Vascular Complications will also be summarized by endovascular procedure type, MANTA device size, and effective puncture size. Procedural causality will be summarized by endovascular procedure type, and device causality will be summarized by MANTA device size.

Additionally, the rate of interventions required to treat Major Complications, Minor Complications, and VARC-2 Major Vascular Complications will be summarized. Overall Major Complication, Minor Complication, and VARC-2 Major Vascular Complication rates will also be summarized by age category, sex, race, and ethnicity categories. Odds ratio estimates (and their CIs) obtained from logistic regression will be used to measure the strength of the association between SFAR and having one of the above complication events.

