### **6.4. Subject Replacement**

See Section 6.5.1 below. A total of 263 subjects will be treated to account for up to a 5% loss to follow-up and to ensure a final Analysis Cohort of 250 subjects with 30 days of follow-up (that is, who meet the primary safety endpoint).

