2.4 Primary Study Hypotheses

2.4.1 Primary Safety Hypothesis

The primary safety hypothesis is that the rate of Major Complications in the Primary Analysis Cohort (the proportion of subjects with one or more Major Complications as defined in Section 2.5.1 below) within 30 days of the procedure is less than the Performance Goal of 19.9%. This Performance Goal was derived from data in the published literature on the use of single or multiple Proglide/Prostar devices in large-bore procedures and from the clinical judgment of expert advisors.

Null hypothesis: The rate of Major Complications within 30 days of the procedure is not less than the Performance Goal of 19.9%.

$$H_0: \pi \geq 0.199$$

Alternative hypothesis: The rate of Major Complications within 30 days of the procedure is less than the Performance Goal of 19.9%.

$H_A: \pi < 0.199$,

where π is the population Major Complication rate. The rate of Major Complications in subjects treated with the MANTA device within 30 days will be presented along with the exact one-sided upper 97.5% confidence bound. If this upper confidence bound is less than 19.9%, the study will have met its primary safety objective.

If more than 13 of the subjects in the Primary Analysis Cohort (5% of the 250 assumed to achieve statistical power) are lost to follow-up or die due to a reason other than a Major Complication, the Major Complication rate will also be estimated from a Kaplan-Meier rate statistical curve. Subjects lost to follow-up will be censored at the date of their last contact. Subjects who die due to a reason other than a Major Complication will be censored at their date of death. An asymptotic one-sided upper 97.5% confidence bound will be placed on the estimated major complication rate at 30 days using the estimated survival curve and the standard error formula given by Peto, Peto, and Armitage¹ in Statistical Note 6. If this upper confidence bound is less than 19.9%, the study will have met its primary safety objective.

In addition, the proportion of subjects with each individual Major Complication will be presented along with their two-sided exact 95% confidence intervals.

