3 DETERMINATION OF SAMPLE SIZE

The sample size for this study was based on the primary effectiveness and safety endpoints of Time to Hemostasis and major complication rate. The population Time to Hemostasis is assumed to be 6 minutes, with a standard deviation of 11 minutes. Based on these assumptions and a normal distribution, 62 subjects will provide 80% power to reject the primary effectiveness hypothesis at a one-sided significance of 0.025.

The population Major Complication rate is assumed to be 13%. Based on this assumption, 250 subjects will provide 80% power to reject the primary safety hypothesis at a one-sided significance of 0.025. Therefore, the necessary sample size is driven by the primary safety endpoint and is 250 subjects.

Assuming a lost to follow-up rate of approximately 5%, the study will treat a total of 263 subjects to ensure an adequate sample size of 250 subjects meeting the 30-day primary safety endpoint.

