5 DATA CONVENTIONS AND DEFINITIONS

5.1 Handling of Missing Data

Missing data will not be imputed for safety endpoints. However, if more than 13 subjects in the Primary Analysis Cohort either die for a reason other than a Major Complication or are lost to follow up within 30 days of treatment, then the rate of Major Complications will also be estimated by the Kaplan-Meier method, to allow for subjects who are censored before a Major Complication can be observed. See Section 2.4.1 for further details.

For effectiveness endpoints, it is highly unlikely that there will be missing data for Time to Hemostasis, Technical Success, Ambulation Success, Time to Ambulation, Treatment Success or Procedure Time. However, if any of these data are missing (i.e., in the event that Time to Hemostasis cannot be evaluated because a surgical repair must be performed), the worst value observed for any subject at the same study site within each analysis cohort, will be imputed for the missing value. Missing data for a subject in the Primary Analysis Cohort will be imputed with the worst value observed for any Primary Analysis Cohort subject at the same study site, and missing data for a subject in the Roll-In Cohort will be imputed with the worst value observed for any roll-in subject at the same study site.

No other imputations will be carried out for missing data.

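### At the planned 5% loss, a subject lost before day 30 with no recorded Major Complication counts as event-free in the primary safety test, and above that loss the SAP does not say which bound decides.

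*SAP*

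**What the plan says.** - **Rate and decision.** SAP 6.3.2: "The Major Complication rate is defined to be the proportion of subjects in the safety evaluation set with one or more Major Complications". The decision rule follows: "If this confidence bound is less than 19.9%, the study will have met its primary safety objective". SAP 2.4.1 specifies that the rate "will be presented along with the exact one-sided upper 97.5% confidence bound".
- **Denominator.** SAP 4.3 puts every non-roll-in subject with attempted use in the Safety Evaluation Set and sets no follow-up condition.
- **Missing data.** SAP 5.1: "Missing data will not be imputed for safety endpoints".
- **Design intent.** Protocol 6.4 has 263 subjects treated "to ensure a final Analysis Cohort of 250 subjects with 30 days of follow-up".
- **Kaplan-Meier.** SAP 2.4.1 gives the trigger: "If more than 13 of the subjects in the Primary Analysis Cohort" are lost or die of another cause, a Kaplan-Meier rate is estimated in addition to the crude one. SAP 5.1 repeats the count, and 6.3.2 gives it as more than 5%. The Kaplan-Meier bound has its own success sentence. SAP 2.4.1 calls that bound asymptotic and 6.3.2 calls it exact, although both cite the same Peto formula.
- **Supportive check.** SAP 4.2 makes a missing 30-day visit a major deviation, and the Per Protocol analysis covers the primary safety endpoint as support only.

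**The concern.** The study is sized on 250 subjects with 30-day data, and the extra 13 are there to absorb losses. The decision rule then divides by all 263, so the allowance for loss enters the test as event-free subjects wherever no event was recorded first. The error runs in one direction, in favour of the device, on the endpoint that decides safety success in a single-arm pivotal study.

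The Kaplan-Meier safeguard starts only above the loss the plan expects. Its trigger names losses and deaths. Voluntary and investigator withdrawals are separate discontinuation categories (Protocol 6.5.4, SAP 6.1.1) and are not named. Once triggered, the estimate adds a second route to success without a rule for disagreement. No tipping-point or worst-case analysis is planned for this endpoint.

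**Working it through.** **Inputs.** Performance Goal 19.9%, assumed rate 13%, one-sided 0.025, 250 evaluable, 263 treated, about 5% lost (SAP 2.4.1 and 3). The exact bound is read as Clopper-Pearson. The share g of the lost subjects' events that were recorded before loss is not in the documents. It is an assumption, shown from 0 to 100%.

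**1. The plan's own figure.** The SAP states: "250 subjects will provide 80% power to reject the primary safety hypothesis at a one-sided significance of 0.025". The upper bound for x events in n is U(x, n) = the 0.975 quantile of Beta(x+1, n−x), and success requires U < 0.199.
- n = 250: U(37) = 19.8% and U(38) = 20.3%, so at most 37 events pass. Error P(X ≤ 37 | 250, 0.199) = 2.32%. Power P(X ≤ 37 | 250, 0.13) = 82.7%.
- The smallest n from which exact power stays at or above 80% is 249. The normal approximation gives 239, or 253 with continuity correction. The 250 is reproduced.
- 250 × 1.05 = 262.5, which gives the 263 treated.

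**2. The rule as written, nobody lost.** n = 263: U(39) = 19.7%, so at most 39 events pass, with error 2.09%.

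**3. The rule as written, m lost.** The recorded count is Bin(263−m, 0.199) + Bin(m, 0.199·g), and false success is P(count ≤ 39).

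With g = 0:

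| m lost | 0 | 2 | 3 | 5 | 8 | 10 | 13 |
|---|---|---|---|---|---|---|---|
| Error | 2.09% | 2.40% | 2.57% | 2.94% | 3.58% | 4.07% | 4.91% |

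With m = 13:

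| Share of events seen before loss | 0% | 25% | 50% | 75% | 80% | 90% | 100% |
|---|---|---|---|---|---|---|---|
| Error | 4.91% | 4.02% | 3.27% | 2.63% | 2.51% | 2.29% | 2.09% |

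The nominal 2.5% is passed when about 80% or less of the lost subjects' events were seen.

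**4. What this means for one result.** Suppose 13 are lost with no event recorded among them. Then 39 events pass on 263 (14.8%, bound 19.7%) but fail on 250 (39/250 = 15.6%, bound 20.7%). With 38 events the bounds are 19.3% and 20.3%. On the 263 scale, x observed events fail once 40 − x lost subjects are assumed to have had an event. At 34 observed events (about 13% of 263) that is 40 − 34 = 6 of the 13. At 39 it is 1.

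**5. Candidate repairs, 13 lost.**
- *Kaplan-Meier at 30 days, by simulation with loss unrelated to event risk.* A log-log bound, or an exact bound on the effective sample size, gave error of about 2.0–2.3% and power of about 82–84% at 13%. A plain symmetric bound with the Peto standard error gave error of about 3.2–3.6%.
- *Denominator of subjects with an event or a completed 30 days.* This keeps lost subjects who had an event and drops those who did not. The expected rate is (250 × 0.199 + 13 × 0.199g) / (250 + 13 × 0.199g), which is 20.3% at g = 0.5 and 20.6% at g = 0.8 against a true 19.9%. Power at 13% falls to 78.2% and 75.4%.

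**The case against.** The case for leaving the rule alone is that early capture is probably high. In the EU pre-market study all 3 Major Complications were in the subjects without hemostasis success (Protocol 1.4), and Protocol 7.7 requires duplex ultrasound by discharge or 48 hours. With 90% of events seen, the error is 2.29%. This stands as a limit on size, but not as proof. It rests on three events. Permanent nerve injury is defined by lasting more than 30 days, so without surgical repair it cannot be established in someone lost earlier, and infection can arise after discharge.

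A reader might infer three stronger things that the documents do not support.
- *That every subject lost or dead before day 30 is scored a success.* An event recorded before loss counts as an event. Subjects who die of another cause have known status up to death, and counting them as non-events is a defensible crude 30-day incidence.
- *That the EU deaths (4 of 50) should be added to the missing count.* Those deaths come from 60-day follow-up, while this endpoint is at 30 days, and death is not unknown status.
- *That the crude result prevails whatever Kaplan-Meier shows.* The SAP does not say which governs. In Protocol 8.3.3 the only safety success sentence follows the Kaplan-Meier bound.

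The Per Protocol analysis is a real check on missing 30-day visits. It also applies other exclusions and does not decide success.

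**Conclusion.** The point holds in limited form. As written, the primary safety test treats lost subjects with no recorded event as event-free, and at the planned 5% loss nothing in the deciding analysis adjusts for it. With 263 treated, 13 lost to follow-up and a true rate of 19.9%, the false-success rate is between 2.1% (all their events seen) and 4.9% (none seen), with 3.3% at half seen and 2.5% at 80% seen. The 4.9% is an extreme bound, and the practical effect is small if most events occur around the procedure. These figures assume a Clopper-Pearson bound and that lost subjects have the same true event rate as the rest.

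The unstated precedence between the two bounds above 13 lost or dead is a separate gap that does not depend on event timing.

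**What to change.** In SAP 2.4.1, 5.1 and 6.3.2:

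1. Make the 30-day Kaplan-Meier estimate the single deciding primary safety analysis whatever the number missing. Censor losses and withdrawals at last contact, and keep the SAP's existing censoring of other-cause deaths at the date of death.
2. Name a bound that holds its level, such as log-log or exact on the effective sample size. Remove the conflict between asymptotic and exact. Do not use the plain symmetric bound with the Peto standard error, which exceeds 2.5% in simulation.
3. Report the crude rate and its bound as secondary, without a success sentence.
4. Add a tipping-point table of how many lost subjects would need an event for the bound to reach 19.9%. Kaplan-Meier assumes that loss is unrelated to risk, and this table tests that assumption.

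Do not switch to a denominator of subjects with an event or completed 30 days. It biases the rate upward and takes power below the planned 80%.

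The cost is SAP wording, somewhat more analysis and one table, and the reported rate and bound become slightly less favourable. No extra subjects or visits are needed, and planned power is kept.

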7 ADJUDICATION OF CLINICAL ENDPOINTS

The Clinical Events Committee (CEC) will review individual adverse events that meet the following criteria:

- Adverse events that are categorized by the investigator on the eCRF as “associated with the target artery and/or the ipsilateral leg (not the contralateral side)”; OR
- Adverse events in the other two categories (“associated with the contralateral access site” or “systemic adverse events”) that are categorized by the investigator as possibly, probably or definitely device-related.

In addition, the medical monitor will review programmed listings for all AEs that are not captured by the criteria above to identify any additional AEs that appear to meet the endpoint definitions and should be reviewed and adjudicated by the CEC. All adverse events reported will be adjudicated as to whether they were device or procedure related by the CEC. Device relationship may be changed after adjudication. The CEC will determine if each reviewed adverse event meets the definition of a Major Complication or a Minor Complication or neither definition. In addition, the CEC will adjudicate each AE as to whether it is a VARC-2 Major Vascular Complication.

Analysis of the primary and secondary safety endpoints will be based on CEC-adjudicated data. The decisions of the CEC will overrule those of the Investigator for endpoint analyses.

8 CHANGES IN THE PLANNED ANALYSES

Not applicable.
